- List of abbreviations, Section 4.1.3.1, Section 6.5.2 and Section 6.5.3: Drug Supply Management replaced with Global Clinical Supply as per name change at Novartis.
- Protocol Summary, Section 6.1, Section 6.6.1, Table 6-3 and Table 6-4: clarified as 20 mg tablets supplied depending on availability.
- Section 4.1.5, Section 6.1.5: revised to extend the duration of the optional extension period and study and to include the transition timeframe to the long-term safety follow-up study or local alternative treatment option.
- Section 4.3: revised to extend the duration of the optional extension period and study.
- Section 6.5.3: corrected that the bioanalyst and the bioanalytical study monitor will also be unblinded in line with Novartis standards.
- Section 7.1.1 and Table 7-1: reference added to the Inclusion/Exclusion criteria for the eligibility assessment at screening.
- Section 7.2.1.3: revised as there was an incorrect reference to the BMI matching for the BMD T-score.
- Section 7.2.2.5, Section 10.5.3: added the central Pituitary MRI/CT assessment for tumor re-occurrence and tumor invasiveness.
- Section 7.2.3.2: corrected as placebo samples will be analyzed for this trial.
- Section 10: clarified that in this section SAS stands for Statistical Analysis System.

IRBs/IECs

A copy of this amended protocol will be sent to the Institutional Review Board (IRBs)/Independent Ethics Committee (IECs) and Health Authorities.

The changes described in this amended protocol require IRB/IEC approval prior to implementation.

The changes herein affect the Informed Consent. Sites are required to update and submit for approval a revised Informed Consent that takes into account the changes described in this protocol amendment.

Amendment 4 (06-Jul-2017)

Amendment rationale

As of 22 March 2017, 137 patients have been enrolled (treated). The study enrollment has been completed.

The main purpose of this amendment is to further increase the duration of the optional extension period in order to collect additional long-term safety and efficacy data as well as to provide continued access to the study drug for those patients benefitting from the treatment until a separate long-term safety follow-up study is set up at participating sites. Based on this extension, the end of study definition has been updated. In addition, the long-term safety follow-up study modalities have been detailed.

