In Part II, 17 out of 19 patients completed the 22 weeks treatment period and 15 of 19 (79%) had normal mUFC levels at week 22. During treatment with LCI699, the mean mUFC levels decreased quickly and stabilized to a normal level (11 to 138 nmol/24h) at Week 4 (Figure 1-5). After Week 4, normal mean mUFC levels were observed through the study up to Week 22. All patients attained UFC normalization at least once during the study, and no patient “escaped” UFC control.

Figure 1-5 Mean (+/-SE) mUFC (nmol/24h) over time by cohort

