4.1.3.2 Eligibility for randomization

In order to be eligible for randomization, patients must have completed dose titration during the first 12 weeks, continued on LCI699 treatment with no further dose increase during Weeks 13-24, and have normal UFC (mUFC \leq ULN) from urine samples collected at Week 24. Decreases or temporary interruptions in the dose of LCI699 for safety reasons are permitted and does not affect eligibility for randomization. Randomization is implemented at the Week 26 visit.

Patients that are not eligible for randomization include: partial responders (mUFC reduced by $\geq 50\%$ from baseline, but above ULN) at Week 24, non-responders (mUFC reduced by $< 50\%$ from baseline and $> ULN$) at Week 24, and any patient whose dose was increased above the level established at the end of Week 12 (dose titration) between Week 13 and Week 24. These patients are followed on open-label LCI699 until the end of the core treatment (Week 48), unless there is a reason to discontinue from the study prematurely.

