4.1.6 Escape

Escape is defined as loss of control of UFC after prior UFC normalization in patients who have completed the dose titration period (Period 1). The following criteria have to be met:

[figure not shown]
- prior normalization of mUFC has occurred ($mUFC \leq ULN$)
- both the mean UFC and at least 2 individual values contributing to that mUFC have to be $>1.5 \times ULN$
- the escape is not related to a dose interruption or dose reduction due to safety reasons

Patients that are randomized to placebo will not be assessed for escape.

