7.1.3 Treatment period

Treatment period is divided in 4 study periods as described in [Section 4.1](#). Patients should be seen for all visits on the designated day with a visit window of ± 3 days and in a fasting state.

During study period 1 (Week 1 to 12), patients will come to the site every 2 weeks. Between visits, they may be contacted by the Investigator/designee in order to increase or decrease the study drug dose based on UFC results from previous visit.

During study period 2 (Week 13 to 24), patients will come to site every 4 weeks. Although study drug dose usually remains stable during this period, adjustment may be needed based on mUFC results and for safety.

Blood samples will be collected for all patients for sparse PK purpose throughout the core study (week 1 – 48). Pharmacokinetic blood collection for a subset of approximately 20 patients will be carried out for extensive PK assessment.

During study period 3 (Week 26 to 34), patients will either continue LCI699 open label if they are not randomized and will have visits every 4 weeks; or will be randomized to one of the 2 arms and will come to site every 2 weeks.

During study period 4 (Week 35 to 48), patients will come to site every 4 weeks.

During study periods 3 and 4, patients are also allowed to have unscheduled visits at any time if they report symptoms of hypercortisolism and have their dose adjusted accordingly.

For details of assessments, please refer to [Table 7-1](#) to [Table 7-5](#) depending on study period.

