1.2 Study design

This is a Phase III, multi-center, double-blind, randomized withdrawal study following a 24 week, single-arm, open-label dose titration and treatment period to evaluate the safety and efficacy of LCI699 for the treatment of patients with Cushing’s disease. The study has a core phase (consists of four study periods 1-4, see schematic diagram below) and an optional extension period, which are described below.

Figure 1-1 Schematic of core study design

[figure not shown]
*To be eligible for randomization, the patient must have mUFC \leq ULN at Week 24, and no further dose increase after Week 12.

**Strata are determined by the combination of two stratification factors at randomization: 1) LCI699 dose at Week 24 (\leq 5mg bid vs. > 5mg bid), and 2) history of pituitary irradiation (yes/no).

1.2.1 Study Period 1

This single-arm, open-label LCI699 period (Week 1 to Week 12) is the individual patient dose titration period.

Figure 1-2 Schematic of study period 1

Dose adjustments are based on the mean of three 24-hour UFC (mUFC) values as measured by the central lab. The triplicate urine samples are collected every two weeks during individual dose titration with the last urine sample preferably collected the day prior to the visit at site. The dose is increased if mUFC is above normal ($> \text{ULN}$). The dose is reduced if $\text{mUFC} < \text{LLN}$, or if the patient is symptomatic and mUFC is in the lower part of the normal range. The dose should be maintained if mUFC is within the normal range and the patient does not have signs or symptoms of adrenal insufficiency. At Week 0 and Week 2, dose increase is not permitted.

1.2.2 Study Period 2

This period (Week 13 to Week 26) aims to assess the efficacy and safety of LCI699 at the therapeutic dose determined during the dose titration period. Patients whose mUFC becomes elevated during this period can have their LCI699 dose increased further, if it is tolerated and the maximum dose of 30 mg b.i.d. has not been reached. Such patients will be followed for long-term safety but will not be considered complete responders, and cannot be randomized. Dose reductions and temporary dose interruptions for safety reasons are permitted during this period without affecting eligibility for randomization.

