2.7 Analysis of secondary efficacy objectives

For the objectives identified below, the definition of Baseline/Randomization assessment and the method of computing confidence intervals are specified in Section [2.1.1.2](#) and Section [2.1.1.8](#) respectively. Last observation carried forward (LOCF) method will not be used in any of these analyses. For analysis using FAS, results will be presented by LCI699 group, Placebo group, Non-randomized patients, and All patients.

2.7.1 Compare the time-to-last control of mUFC during the randomized withdrawal period between patients randomized to continued LCI699 and placebo

The results of this objective were reported in the interim CSR, and will not be repeated for the Final CSR.

2.7.2 Assess the complete, partial, and overall response rate at Week 12, Week 24, Week 48, and during the extension period

The proportion of complete responders (enrolled patients with $mUFC \leq ULN$), partial responders (enrolled patients with $mUFC > ULN$ and at least 50% reduction from baseline), and overall responders (enrolled patients with $mUFC \leq ULN$ or have at least 50% reduction from baseline) will be summarized using point estimates for every scheduled visit in the core and extension (provided [adequate follow-up](#)) at which UFC is collected. 95% 2-sided CIs for response rates will be provided for Week 48, Week 60, Week 72 and the last available assessment of the study. The FAS will be used for the analyses.

2.7.3 Assess the change in mUFC during the core and extension period of study

For the actual value and change in mUFC from baseline during the overall study period, descriptive summaries will be provided for every scheduled visit in the core and extension (provided [adequate follow-up](#)) at which UFC is collected. The FAS will be used for the analysis.

Patients randomized to placebo during the RW period, will not have their mUFC values included in the analysis for visits at which they received placebo.

2.7.4 Assess the change in cardiovascular-related metabolic parameters associated with Cushing's disease during the core and extension period of the study

The following parameters will be analyzed: glucose, HbA1c, fasting lipid profile, SBP, DBP, weight, waist circumference and BMI).

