2.7.7 Assess the time-to-escape under treatment of LCI699

Escape is defined as the first loss of control of UFC that meets all of the following criteria:

- prior normalization of UFC has occurred ($mUFC \leq ULN$)
- both the $mUFC$ and at least 2 individual values contributing to that $mUFC$ have to be $>1.5 \times ULN$
- the loss of control of UFC is not related to a dose interruption or dose reduction due to safety reasons
- happens beyond 12-week dose titration period (Study Period 1).

Time-to-escape is defined as the time (in days) between the first UFC assessment with $mUFC \leq ULN$ and either the UFC assessment of escape (event) or last UFC assessment before permanent discontinuation of LCI699 treatment (censored), whichever occurs earlier.

For patients who attained normalization of UFC ($mUFC \leq ULN$), time-to-escape will be analyzed using K-M plot. The quartiles of time to escape and corresponding two-sided 95% confidence interval will be calculated using Kaplan-Meier methodology. In addition, time-to-escape will be summarized using descriptive statistics for patients who escape. FAS will be used for the analysis.

Patients randomized to placebo are not included in this analysis.

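### Time-to-escape drops placebo-randomized patients altogether, losing their LCI699 time up to Week 26 and overstating pooled escape when early escapes fall mainly in non-randomized patients

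*SAP*

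**What the plan says.** SAP 2.7.7 counts an escape only beyond the 12-week titration period. It measures time from the first mUFC at or below ULN and censors at the last UFC assessment before permanent LCI699 discontinuation. It uses the FAS and ends: "Patients randomized to placebo are not included in this analysis". Protocol 10.5.2.7 has the same rule, and Protocol 4.1.6 says: "Patients that are randomized to placebo will not be assessed for escape". None of the three places sets a time limit on the exclusion.

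To be randomized at Week 26, a patient must have "continued on LCI699 treatment with no further dose increase during Weeks 13-24" and have mUFC at or below ULN at Week 24 (Protocol 4.1.3.2). Under SAP 1.2.2, patients whose dose is raised in Period 2 because mUFC became elevated "will not be considered complete responders, and cannot be randomized". Allocation is 1:1 (Protocol 4.1.3.3).

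SAP 2.7 adds: "For analysis using FAS, results will be presented by LCI699 group, Placebo group, Non-randomized patients, and All patients".

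Elsewhere the SAP removes only the placebo time. Response rates (2.1.1.7), mUFC change (2.7.3), cardiovascular-related parameters (2.7.4) and the safety summaries (2.8) keep these patients and omit what was measured or began while they were on placebo.

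**The concern.** Whether a patient enters the curve depends on an allocation at Week 26. That is after the clock has started and up to 14 weeks (26 - 12) after escapes become countable. The patients removed have all been shown to be controlled at Week 24. The patients who lost control and were up-titrated all stay in. This is selection on a future event, and it pushes the pooled Kaplan-Meier curve upward whenever early escapes occur mainly in non-randomized patients. The design favours that condition, because a patient well above ULN at Week 16 or 20 would usually be up-titrated or fail the Week 24 criterion.

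There is also a reporting conflict. Section 2.7.7 does not itself name a pooled curve, but 2.7 promises FAS results for the Placebo group and for All patients. Under 2.7.7 the first is empty and the second lacks one randomized arm.

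Control without dose escalation for therapeutic escape is a stated aim of the design (Protocol 2.2). The pooled curve would show more, and possibly earlier, escape than occurred on LCI699.

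**Working it through.** **Inputs.** The planned arm size is 33, with 132 enrolled and 50% eligible for randomization (Protocol 10.8, SAP 3.1). The number treated is 137 (Protocol, Amendment 4 rationale). The documents give neither an escape rate for this trial nor N, the number who normalise. Both are assumptions here, with N taken as 100-137.

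**The plan's own figure.** There is none for time-to-escape. The 33 per arm comes from the power statement of 87% for 70% versus 30% at two-sided 0.05. Recalculated, this is 92.0% without and 87.3% with continuity correction, and 87.4% by simulation of the exact stratified test. The 33 is therefore a sound input.

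**Early escape, pooled.** Let R patients be randomized and M be non-randomized patients who normalised, with escape risks qR and qM before Week 26.

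- All LCI699 time kept: (M·qM + R·qR)/(M + R)
- Rule in 2.7.7: (M·qM + 0.5·R·qR)/(M + 0.5·R)

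With M = R = 66:

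| qM | qR | All kept | 2.7.7 | Ratio |
|---|---|---|---|---|
| 20% | 0% | 13.2/132 = 10.0% | 13.2/99 = 13.3% | 1.33 |
| 20% | 5% | 16.5/132 = 12.5% | 14.85/99 = 15.0% | 1.20 |
| 10% | 10% | 10.0% | 10.0% | 1.00 |
| 5% | 10% | 9.9/132 = 7.5% | 6.6/99 = 6.7% | 0.89 |

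The condition on where early escapes fall is therefore needed. When qR = 0 the ratio is N/(N-33): 137/104 = 1.32, 132/99 = 1.33, 100/67 = 1.49.

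**Range of escape rates.** The only observation in the documents is from the earlier study, where "no patient “escaped” UFC control" among 19 patients over 22 weeks (Protocol 1.2.1.2.2). The exact 95% upper limit is 1 - 0.025^(1/19) = 17.6%. Per 4 weeks this is 1 - (1 - 0.176)^(4/22) = 3.5%. Rates of 0.5-3% per 4 weeks were therefore examined.

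**Simulation** (2000 trials per setting; standard error of planned minus true at most 0.07 points). First normal mUFC falls at Weeks 2-12. Escape is countable after Week 12 at the scheduled mUFC visits. Sixty-six patients are drawn from those escape-free at Week 24 and split 33:33. Equal hazards, N=137, risk in % at 24/48/72 weeks from first normal mUFC:

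| Rate per 4 weeks | True | Under 2.7.7 |
|---|---|---|
| 0.5% | 2.3/4.6/7.5 | 2.7/5.1/7.9 |
| 1% | 4.6/9.1/14.4 | 5.4/10.0/15.2 |
| 2% | 9.1/17.5/27.0 | 10.8/19.2/28.5 |
| 3% | 13.2/25.1/37.7 | 15.8/27.4/39.6 |

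Two further cases used gamma-distributed hazards with coefficient of variation 1, with a random draw or a draw favouring low-hazard patients. Over all cases and N=100-137, planned minus true is 0.5-1.5 points at 0.5%, 0.8-2.8 at 1%, 1.5-4.7 at 2% and 1.9-5.7 at 3%. The largest case (N=100, 3%, low-hazard draw) gives true 12.3/22.3/32.0 and planned 16.6/27.5/37.8. Adding 1% dropout per 4 weeks (N=137, random draw) leaves gaps of 0.5-0.6, 0.7-0.9, 1.5-1.9 and 2.0-2.6 points for the four rates.

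**Lower quartile.** At 0.5-1% the median lower quartile is not reached by Week 96. At 2-3% it falls 4-14 weeks too early, for example 64 instead of 68 weeks (equal hazards, N=137, 2%) and 40 instead of 54 (N=100, 3%, low-hazard draw).

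**Censoring at placebo start.** The error is at most 0.2 points if those randomized are a random subset of the patients controlled at Week 24. If the draw favours low-risk patients, it is at most 0.4 points at 24 weeks and 0.7-2.8 at 72 weeks; the largest case gives 12.7/24.1/34.8. A separately programmed simulation agreed: for N=137 at 2%, true 9.1/17.6/27.1, planned 10.8/19.1/28.5, censored 9.1/17.6/27.2.

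**The case against.** The exclusion is pre-specified and deliberate, and the SAP follows the protocol. The analysis is supportive with no formal test (SAP 2.1), and the bias is conservative. Changing it now favours the drug after unblinding. The Week 12-26 data of these patients still count in the key secondary endpoint and in the visit-level response and mUFC summaries. The separate LCI699-group and non-randomized curves are unaffected. All of this stands. It limits the importance of the point and shapes the remedy.

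The size is also open to challenge. The factors 1.32-1.49 assume no early escape in the placebo arm. A dose increase is triggered by mUFC above ULN, whereas escape needs the mean and two samples above 1.5 x ULN, so being non-randomized is not the same as having escaped. The earlier study's 22 weeks include titration, so its 3.5% limit transfers only roughly. Against simple binomial 95% half-widths for 104 patients, the tabulated equal-hazards gaps are 8-37% of the half-width, and the largest case is about half of its own (67 patients). These are fair limits on size. They do not affect the direction, and a bias that extra patients would not remove is not excused by imprecision.

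It can be said that the closing sentence of 2.7.7 already explains the empty Placebo column. It does give the reason, but not what a column labelled All patients then contains.

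Simple censoring does leave some bias, because only controlled patients are censored at Week 26. In the largest case 2.8 points remain at 72 weeks. That is about half of the error under the present rule, and much less remains in the other cases.

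**Conclusion.** The concern holds. Removing placebo time is right; removing the earlier LCI699 time is unnecessary and selects on a future event. The upward direction follows if early escapes occur mainly in non-randomized patients, which the eligibility rules make likely but not certain. The size rests on assumed escape rates, an assumed N of 100-137 and the planned 33 per arm: about 0.5 to 5.7 percentage points over 24-72 weeks for rates of 0.5-3% per 4 weeks. The lower quartile is affected only at the higher rates. Error control and the primary and key secondary results are untouched. The point should be corrected, but it does not threaten the trial's main conclusions.

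**What to change.** In the pooled analysis, include every FAS patient who attained mUFC at or below ULN. Count any escape before placebo starts. Censor placebo-randomized patients at their last mUFC before the first dose of randomized treatment, whatever its date. The 21-day randomization value of SAP 2.1.1.2 should not be used for this, since it can be missing. Keep the protocol's clock start.

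The core phase was unblinded on 10-May-2018. Either record this in SAP Section 4 as a change made after unblinding, or report it as a labelled sensitivity analysis. In both cases show the pre-specified result beside it. State in 2.7.7 what the Placebo and All patients columns contain.

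Optionally, a further sensitivity analysis can give the LCI699 arm weight 2 from randomization, with robust or bootstrap confidence intervals. In the largest simulated case this returned the true 12.3/22.3/32.0. It is not essential.

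The cost is one paragraph in 2.7.7, one entry in Section 4 and one more Kaplan-Meier output from existing data. Only the optional weighting needs appreciable programming. The drawback is that the change favours the drug and comes late, which is why the original result must remain in view.

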2.8 Safety analyses

The assessment of safety will be based mainly on the frequency of adverse events and on the number of laboratory values that fall outside the pre-determined ranges. Other safety data (e.g. electrocardiogram, vital signs, and special tests) will also be presented.

In the Final CSR results for the overall study period will be analyzed, using the SAS. Results will be presented by Randomized patients, Non-randomized patients and All patients.

The safety results for the Final CSR will focus solely on the safety of LCI699. Therefore scheduled safety assessments performed whilst on placebo, for patients randomized to placebo during the RW period, will not be included. Similarly, adverse events with a start date which corresponds to when a patient was receiving placebo will not be included in adverse event summaries.

